1.3 Research Design and Methods

The study will take place in 4 phases, each utilizing methodology specific to the phase. Phases are created to improve clarity of expectations for participants entering at different points in the study and clarity of the general research protocol.

- PHASE 1: Refine objective data capture techniques. Key to any VR intervention is the ability to monitor and quantify work productivity behaviors and to establish an accurate baseline. This has been done with adult workers, but we will need to refine the keyboard and mouse click algorithms for use with emerging adults (aged 18-25 years) with ADHD who are completing real homework assignments and studying (n=30 to complete the phase). The study design for this phase will follow an AABBAABB design – where A is passthrough control and B is the immersive VR environment. In this way, each participant essentially serves as their own control as they switch between passthrough and VR immersion sessions. The team will also explore whether adding in eye gaze tracking and periodic screenshots improves the accuracy of the algorithms.
- PHASE 2: Develop and refine contingency management algorithms. Once data capture capabilities have been confirmed in emerging adults with ADHD, we must test the ability to combine these data into an algorithm to provide real-time performance feedback to participants and contingency management (n=30 to complete the phase). As with Phase 1, the study design for this phase will follow an AABBAABB type design – where A is passthrough control and B is the immersive VR environment. In this way, each participant essentially serves as their own control as they switch between passthrough and VR immersion sessions. The team will also conduct focus groups to determine ways to improve feasibility/usability and to identify strategies and tools that motivate participants to complete work.
- PHASE 3: Pilot test and evaluate impact on target mechanisms. Conduct a small randomized control trial (RCT) to assess the feasibility/usability and preliminary effects of the VR environment alone (n=15) compared to VR environment + contingency management (n=15) and the VR passthrough control (n=15). Proposed mechanisms of action will be measured every session,

including algorithm data plus self-ratings of concentration, homework effort, and homework motivation.

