VR intervention: After completing the initial evaluation and confirming eligibility, a new sample of 45 participants will be randomized to 1 of 3 groups and then scheduled to use the VR headset in their room/home or the library. Randomization will be performed (1:1:1) to the three conditions. Randomization will be blocked on ADHD medication status to ensure an equal number of participants taking and not taking ADHD medication in each group. Phase 3 includes a 2-session baseline where all participants complete homework and study outside of VR (total of 12 sessions; 2 non-VR baseline and 10 in VR condition). During each session, participants will complete a set of standardized reading comprehension problems to determine how many they complete and how accurately. LSU and Rutgers study staff will run VR intervention visits at their respective study sites.

Group 1, VR passthrough: After completing the two session non-VR baseline, participants will use the VR headset in their room/home or the library 10 times over three weeks (max twice a day with a minimum 2-hour break) for 1-hour sessions each time. The participant will wear the headset, but it will not be used as usual. The headset will be in “VR passthrough” mode, meaning the participant will see through to the normal environment and laptop (i.e., they can see the real world around them, just wearing a headset).

Group 2, VR environment only: After completing the two session non-VR baseline, participants will use the VR headset in their room/home or the library 10 times over three weeks (max twice a day with a minimum 2-hour break) for 1-hour sessions each time. The participant will wear the VR headset and engage in homework in the VR environment.

Group 2, VR environment + contingency management: After completing the two session non-VR baseline, participants will use the VR headset in their room/home or the 10 times

over three weeks (max twice a day with a minimum 2-hour break) for 1-hour sessions each time. The participant will wear the VR headset and engage in homework in the VR environment while receiving contingency management (real-time feedback on performance through red or green light FlowLight icon).

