1.5 Sample Size Justification

PHASE 1: Refine objective data capture techniques. 30 participants completing 10 sessions will allow the team to implement and refine the keyboard and mouse click algorithms needed to ensure that we are tracking attention accurately. Since the goal is to refine the algorithms, no control group is needed.

PHASE 2: Develop and refine contingency management algorithms. 30 participants completing 10 sessions will allow for proper testing of the addition of the FlowLight icon (a stoplight) and box showing points earned within the VR environment. The goal is to understand how and when participants like to receive feedback about their on-task behavior and attention. A secondary goal is to understand how best to motivate participants to stay on-task and to complete work efficiently (e.g, a points system). 10 sessions with 30 participants are sufficient for this along with the focus group, and no control group is needed.

PHASE 3: Pilot test and evaluate impact on target mechanisms. 45 participants randomized to 1 of 3 groups will inform the feasibility and usability of the system tested and refined in phases 1 and 2. Though outcome measures will be collected, power analyses are not required due to the pilot status of the trial. The goal of phase 3 is to calculate effect sizes rather than to run statistical tests to begin to understand the magnitude of effects.

PHASE 4: Conduct a parallel group randomized trial. 252 participants randomized to 1 of 3 groups will allow for appropriate comparison across groups. Power calculations were run to determine this sample size. Power calculations are based upon $N = 84$ participants in each condition, for a total sample of 252 college students with ADHD. [name] prior intervention studies focused on improving attention produced effect sizes ranging from .6 to 1.12 comparing treatment to waitlist control. For the purposes of these power analyses, we use an effect size of .8 as the expected effect between the VR environment + contingency management group and passthrough control. This effect is also consistent with meta-analyses of behavioral contingency management interventions. Differences between active intervention conditions in our recent trial ranged between .4 to .6. Accordingly, between group effects (i.e., VR environment only to VR passthrough and to VR environment + contingency management) for the current study were estimated at $d = .4$.

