1.10 Timetable/Schedule of Events

	Sep	Oct	Nov	Jan	March	April	May	Summer Semester
Year 1 R61	Project 1 Recruitment (N=30) Inclusion/exclusion evaluations			Project 1 Intervention Sessions				Analysis and refinement of algorithms and VR protocol
				Project 2 Recruitment (N=30) Inclusion/exclusion evaluations				
Year 2 R61	Project 2 Intervention Sessions Project 3 Recruitment (N=45)			Project 3 Intervention Sessions				Analysis and refinement and evaluation of Go/No-Go
Year 3 R33	RCT Cohort 1 Recruitment (N = 63)			RCT Cohort 2 Recruitment (N=63)				Analysis and dissemination
Year 4 R33	Cohort 2 Intervention RCT Cohort 3 Recruitment (N = 63)			Cohort 3 Intervention Sessions RCT Cohort 4 Recruitment (N=63)				Analysis and dissemination
Year 5 R33	Cohort 4 Intervention Sessions			Analysis and publication				

Note: Total sample = 252; 4 cohorts of 63 participants each; intervention period for each cohort allows for 1 month of cushion for missed and make-up sessions. December is not shown as no activities occur over winter break although the study team can recruit and provide intervention for the first 1.5 weeks in December.
								

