Phase 2: This project incorporates the contingency management procedures. Trends in motivation across sessions will be evaluated in relation to objective and rating scale metrics of attention and to FlowLight data. Focus groups will be audio-recorded and transcribed verbatim. The focus group data will be analyzed inductively for information relevant to feasibility and acceptability of the protocol. Two study personnel will separately code notes taken during the focus groups for emerging concepts and themes. Initial analysis will consist of identifying concepts found within the data through open coding. Inter-rater reliability checks will be used to compare the themes generated. Coding will continue until the point of saturation, that is, when no new concepts emerge. Data will be systematically analyzed according to the principles of thematic analysis, a method commonly used in qualitative research of this nature.

Phase 3. Because these analyses will focus on evaluating preliminary intervention effect sizes, outcome analyses will be conducted separately for each target mechanism. To compare groups, the variable (e.g., objective attention) will be entered analysis of variance (ANOVA), which will yield effect sizes for time and for interactions of time by intervention. The primary dependent variables will be objective assessment of attention and ratings of concentration, as well as ratings of homework effort and homework motivation. We will also compare trajectories of objective attention data across the three conditions.

Phase 4. The mixed model methodology planned and incorporated by the SAS GLIMMIX procedure can accommodate missing response data, thus allowing us to make use of all available data; note that covariate measurements are taken at baseline and should not be missing. Using Bayes' estimation, individuals with more data are given more weight in the calculation. This procedure is preferable in comparison to listwise or pairwise deletion in analyses where portions of the developmental curve are represented by differing individuals. In addition, we will check to see whether missing observations are missing at random, where we will test whether treatment group or any other covariate has an effect on the missing information. Any covariate associated with missing data will be included in the final model. Mediational models

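### The effect sizes named for Phase 3 (time, and three-arm time-by-intervention) do not estimate the arm-versus-arm effects that the pilot is meant to measure; signed pairwise differences with intervals should be named instead

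*Combined protocol and SAP*

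**What the plan says.** Section 1.3 (Phase 3) describes a small randomized trial to assess feasibility, usability and "preliminary effects of the VR environment alone (n=15) compared to VR environment + contingency management (n=15) and the VR passthrough control (n=15"). That is a question about one arm against another. Allocation is equal: "Randomization will be performed (1:1:1) to the three conditions". Each participant has a "total of 12 sessions; 2 non-VR baseline and 10 in VR condition".

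Section 1.5 sets testing aside for this phase: "The goal of phase 3 is to calculate effect sizes rather than to run statistical tests to begin to understand the magnitude of effects". The effect size is therefore the Phase 3 efficacy result.

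Section 6.1 (Phase 3) says how groups are compared: each variable goes separately into an "analysis of variance (ANOVA), which will yield effect sizes for time and for interactions of time by intervention". It names four primary dependent variables: objective attention and ratings of concentration, homework effort and homework motivation. It adds a comparison of trajectories across the three conditions, for objective attention only. It does not name the effect-size index, a pairwise contrast or an interval.

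For Phase 4, section 1.5 works in pairwise standardized differences. It assumes .8 for VR plus contingency management against passthrough. For the other two comparisons it says ("i.e., VR environment only to VR passthrough and to VR environment + contingency management) for the current study were estimated at $d = .4").

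**The concern.** An effect size can stand in for a test only if it estimates the comparison of interest. The two named here do not. A time effect describes average change over everyone, passthrough included. A time-by-intervention effect over three arms says how much the arms differ in their change overall, but not which arm did better or which pair differs.

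The three-arm design exists to separate the contribution of the VR environment from that of contingency management (section 1.4 gives this as the reason for the VR-only arm). If the reported figure cannot make that separation, the pilot's headline result does not answer its own question and cannot be laid beside the planning values for the larger trial.

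**Working it through.** **Inputs.** Three arms of 15, 45 in total (section 1.3); 12 sessions (section 1.3); pairwise d of .8, .4 and .4 (section 1.5). The plan gives no numerical Phase 3 effect size, so there is no figure to reproduce. Assumptions, because the plan is silent: two occasions (before and after), so that the interaction is a one-way ANOVA on change scores with 2 and 42 degrees of freedom; d expressed in change-score SD units; where an index is needed, partial eta-squared.

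**Step 1: sign.** Let f² be the mean squared deviation of the arm effects from their average, with eta-squared = f²/(1 + f²). Arms are ordered passthrough, VR alone, VR plus contingency management.

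- Planned pattern (0, .4, .8): mean .4, deviations −.4, 0, .4, so f² = .32/3 = .1067 and eta-squared = .1067/1.1067 = .096.
- Reverse (.8, .4, 0): the same deviations with signs flipped, so again .096.

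Simulated at 15 per arm, the mean sample partial eta-squared is about .136 for both. The difference between contingency management and passthrough is +.8 in one and −.8 in the other.

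**Step 2: which pair differs.**

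- (0, 0, .4): mean .133, squared deviations sum to .1067, f² = .0356, eta-squared = .034.
- (0, .4, .4): mean .267, the same sum, eta-squared = .034.

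The mean sample value is about .077 for both. VR alone does nothing in the first and accounts for the whole effect in the second.

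**Step 3: behaviour under no effect.** The expected partial eta-squared is df1/(df1 + df2) = 2/(2 + 42) = .045. Using all 12 sessions under sphericity, it is 22/(22 + 462) = .045 again. Omega-squared, which corrects this bias, averages about 0 in the same simulation.

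**Step 4: how far it separates effect from no effect.** Take .06 as an illustrative cut-off; the plan has none. Partial eta-squared reaches .06 with probability 27% under no effect and 80% under the planned pattern (two occasions). With 12 sessions the no-effect figure is 14% to 20%, depending on the within-person correlation structure.

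**Step 5: what pairwise differences would give.** The 95% half-width is 1.96 × √(2/15 + d²/60).

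| True d | Half-width | Interval centred on d |
|---|---|---|
| 0 | 0.716 | −0.72 to 0.72 |
| .4 | 0.723 | −0.32 to 1.12 |
| .8 | 0.744 | 0.06 to 1.54 |

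These are signed, centred on zero when there is no effect, and of the same kind as the Phase 4 planning values.

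**The case against.** **Direction is available anyway.** An ANOVA by arm and time is computed from arm-by-time means, and the trajectories of objective attention would show direction. This stands: the analysis does not hide which arm did better from anyone who looks at the means. But the plan does not name means or contrasts as the result, and trajectories cover one of the four primary variables, without a metric.

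**The index is not named.** The upward bias in Step 3 holds for eta-squared, partial eta-squared and f, and not for omega-squared. That also stands, so the bias is conditional. The lack of sign and of contrast applies to all of them.

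**The noise comes from 15 per arm, and pairwise differences share it.** Under no effect, a single pairwise difference exceeds .4 in absolute value about 27% of the time, and at least one of three does so about half the time. At a true d of .4 the interval excludes zero only about 18% of the time. This is correct. The proposal makes the estimate answer the question; it does not make it precise.

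**Stronger readings that the documents do not support.** A reader might infer that the Phase 3 result cannot tell a working intervention from an inert one. Step 4 shows that it can, though noisily. A reader might also infer that these effect sizes decide whether Phase 4 proceeds. The timetable in section 1.10 schedules "Analysis and refinement and evaluation of Go/No-Go" after the Phase 3 sessions but gives no criterion, and section 1.5 also gives Phase 3 a feasibility and usability purpose. Nor do the documents say that Phase 3 will confirm or re-size Phase 4: the .8 and .4 come from earlier trials and meta-analyses.

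**Conclusion.** The point holds as a mismatch between the Phase 3 aim and the effect sizes named to meet it. The time effect and the omnibus interaction effect do not estimate the pairwise comparisons in section 1.3, and they are not on the scale of the d values in section 1.5. The loss of sign and contrast follows from the three-arm omnibus form and does not depend on the index; the particular values (.096 and .034) assume change-score SD units. The .045 average under no effect rests on an assumed eta-squared-type index. It is a worthwhile, inexpensive improvement to the analysis text. It does not show an error in the Phase 4 sample size or a defect in any stated decision rule.

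**What to change.** In section 6.1, Phase 3, state that for each of the four primary variables the reported effect sizes are three signed standardized differences, each with a 95% confidence interval:

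- VR plus contingency management minus passthrough
- VR alone minus passthrough
- VR plus contingency management minus VR alone

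Compute each (for example as Hedges' g) on the values from the in-condition sessions 3 to 12, adjusted for baseline. Name the baseline: sessions 1 and 2, or the initial-evaluation rating where those sessions collect none. Name the standardizing SD as well. Section 1.5 does not say which SD underlies .8 and .4, so that should be stated too if the figures are to be compared. Keep the ANOVA time and interaction effect sizes as supplementary, with the index named.

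The cost is a few sentences and a few lines of code, with no new data or participants. The drawback is presentational: intervals with half-widths of 0.72 to 0.74 will show plainly how little a pilot of this size can say about magnitude. They should be read as estimates, in keeping with the plan's decision not to test in this phase.

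### The Phase 3 ANOVA names neither its time points nor a rule for missing sessions; a mixed model on all available sessions would protect precision

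*Combined protocol and SAP*

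**What the plan says.** **Method.** Under Phase 3 in section 6.1, each mechanism is analysed separately by an ANOVA that "will yield effect sizes for time and for interactions of time by intervention". On outcomes: "The primary dependent variables will be objective assessment of attention and ratings of concentration, as well as ratings of homework effort and homework motivation". The paragraph ends by promising a comparison of objective-attention trajectories across the three conditions, without a method.

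**Data.** Section 1.3 states: "Proposed mechanisms of action will be measured every session". The Phase 3 procedures in 1.3 A say that "a new sample of 45 participants will be randomized to 1 of 3 groups" and describe a "total of 12 sessions; 2 non-VR baseline and 10 in VR condition". The Phase 3 and 4 list in 1.3 B puts the session measures under ten sessions.

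**Purpose.** Section 1.5 says that "power analyses are not required due to the pilot status of the trial" and that Phase 3 aims at effect sizes, not tests.

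**Missing data.** Section 6.1 opens with a general description of missing-data patterns and dropout. For Phase 4 it adopts a mixed model on all available data and says: "This procedure is preferable in comparison to listwise or pairwise deletion". There is no missing-data rule for Phase 3.

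**The concern.** An analysis with a time effect and a time-by-intervention effect on the same people is a repeated-measures analysis, even though the plan does not use that term. In its classical form it needs a complete row for each participant, so one missing session can remove all of that person's data. With 15 per arm each such loss is expensive, and the effect sizes are Phase 3's main quantitative product.

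Missing sessions are a realistic prospect. Participants may withdraw, and section 1.3 D removes those whose adverse reaction to the headset cannot be resolved. The timetable in 1.10 allows time for missed and make-up sessions in the Phase 4 cohorts. The plan already holds a method that keeps partial records, but assigns it only to the larger trial.

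**Working it through.** The plan gives no missed-session rate, dropout rate or precision target for Phase 3, so there is no figure of its own to reproduce beyond 3 x 15 = 45. What follows is an illustration over an assumed range.

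**Inputs from the plan:** 45 participants, 15 per arm; 12 sessions (1.3 A) or 10 (1.3 B).

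**Assumed:** a probability m of missing any one time point, independent across time points; T time points in the ANOVA; deletion of incomplete cases; a true standardised difference d = 0.4, used only for the interval width.

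**Step 1, expected complete cases** = 45 x (1 - m)^T. At m = 5%:

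- T = 12: 45 x 0.5404 = 24.3
- T = 10: 45 x 0.5987 = 26.9
- T = 2: 45 x 0.9025 = 40.6

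**Step 2, approximate 95% half-width for a pairwise d** = 1.96 x sqrt(2/n + d^2/(4n)), with n complete cases per arm. This treats d as a simple two-group difference.

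- All 15 per arm: 1.96 x sqrt(0.1333 + 0.0027) = 0.72
- 24.3/3 = 8.1 per arm: 1.96 x sqrt(0.2469 + 0.0049) = 0.98
- 40.6/3 = 13.5 per arm: 1.96 x sqrt(0.1481 + 0.0030) = 0.76

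| m | Complete, T = 12 | Complete, T = 10 | Complete, T = 2 | Half-width, T = 12 | Half-width, T = 2 |
|---|---|---|---|---|---|
| 1% | 39.9 | 40.7 | 44.1 | 0.77 | 0.73 |
| 2% | 35.3 | 36.8 | 43.2 | 0.82 | 0.74 |
| 5% | 24.3 | 26.9 | 40.6 | 0.98 | 0.76 |
| 10% | 12.7 | 15.7 | 36.5 | 1.36 | 0.80 |

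**Step 3, deletion against a mixed model.** A small simulation used two arms of 15, 12 sessions (2 baseline, 10 in condition), total SD 1, a true effect of 0.4 and 150 replicates. The mixed model had a random intercept and coded time as baseline versus condition sessions. About two thirds of participants had complete data.

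| Missingness | Listwise: mean (SD) | Mixed model: mean (SD) |
|---|---|---|
| Unrelated to outcome | 0.395 (0.256) | 0.403 (0.199) |
| In one arm, more likely after a low previous score | 0.377 (0.258) | 0.393 (0.190) |

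The variance ratios are (0.256/0.199)^2 = 1.65 and (0.258/0.190)^2 = 1.84, so deletion cost a good deal of information. The Monte Carlo standard error of the listwise mean is about 0.258/sqrt(150) = 0.021, so 0.377 lies about one standard error from 0.4. These settings showed a loss of precision and no upward bias.

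**The case against.** The strongest reply is that the plan never says the ANOVA uses all sessions or that anyone is deleted. Because the trajectory comparison is mentioned separately, the ANOVA could be on baseline versus post, or on averaged sessions, and then the loss is small. This stands as a limit on size. It does not remove the gap, because nothing in the plan says which reading applies.

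The assumed rates may also be too high, and independence is pessimistic: misses clustered within people leave more complete cases. Under 1.3 A, sessions below the length threshold are repeated, and under 4.6 B the last $50 is paid only when all 12 sessions are done. Both reduce isolated misses, but neither recovers someone who withdraws or is removed.

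Further, Phase 3 is a pilot whose estimates are imprecise under any method, with a half-width of about 0.72 even when data are complete. That lowers the stakes, but it is no reason to discard data already collected. Unequal correlations between sessions mainly affect the validity of F-tests, which are not the aim here, so the point does not rest on them.

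Finally, the Phase 4 model cannot be copied across unchanged. It is written for baseline-to-post change with dummy-coded time; with 12 sessions and three conditions that means 36 cell means from 45 people. This is right, and the time coding has to be adapted.

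**Conclusion.** The point holds as a minor one about method. Phase 3 leaves its time points and missing-data handling open, and the usual session-level ANOVA would run against the reasoning that the same section gives for Phase 4. If 5% of time points are missed independently, complete cases range from about 24 of 45 (12 time points) to about 41 (two), and the half-width for d from 0.98 to 0.76, against 0.72 with no loss. These figures rest on assumed rates and on deletion of incomplete cases.

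A reader might infer four stronger things that the documents do not support:

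- **That the plan prescribes deletion.** It does not; deletion is the default behaviour of the classical method.
- **That Phase 4 rejects ANOVA.** It calls its own model preferable to listwise or pairwise deletion and does not mention ANOVA.
- **That these effect sizes are documented inputs to Go/No-Go.** The timetable in 1.10 only places that evaluation after the Phase 3 sessions; no criteria are given.
- **That the estimates would be too favourable.** That would need missingness that is related to outcome and differs by arm. Selection acting alike in all arms gives no reason to expect an inflated contrast.

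**What to change.** In section 6.1, replace the Phase 3 ANOVA with a mixed-effects model for each mechanism, fitted to all randomised participants and all their available sessions.

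- **Time coding:** keep it parsimonious, for example baseline sessions versus condition sessions (3 x 2 = 6 cell means), or a linear session trend, and not 12 dummy levels.
- **Reporting:** give standardised condition-by-time effects with 95% intervals, state which SD is used to standardise, and report the number of participants and sessions contributing per arm.
- **Trajectories:** use the same model for the planned comparison of objective attention, which has no method at present.

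If the ANOVA is kept, the plan should at least name its time points and its missing-data rule.

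The cost is minor SAP wording, with no new data collection. The mixed model relies on data being missing at random, so reasons for missed sessions and withdrawals should be tabulated by arm.
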